4. METHODOLOGY

4.1. Design

Experimental, randomized, with a control group without intervention.

4.2. Study population

It will be made up of women belonging to the VII health area of the Principality of Asturias, aged between 25 and 45 years, without a previous diagnosis of BC.

All women who give written consent to participate in the study will be included. Those who: (i) do not have adequate physical or psychological characteristics to participate in the study will be excluded; (ii) do not have the means to regularly access the web-app that will be used to carry out the educational intervention; (iii) your contact by email is not possible.

The recruitment of women will be carried out, between the months of January and February 2022, by sending a letter of invitation to participate from the health area. A random sample of 361 women will be sufficient to estimate, with 95% confidence and an accuracy of +/- 5 percentage units, a population percentage that is expected to be approximately 75%. The percentage of necessary replacements has been predicted to be 20%.

The health area VII technician and member of the research team ([name]) will draw up a list of all the women likely to be included in the study. The members of the research team prepare a letter for each of the women and they will be sent from the management of Sanitary Area VII to the women by postal mail.

The letter contains a contact email to which they will write if they are interested in participating. The women will be answered as the emails are received and when we have obtained the necessary sample, the project will be explained in detail with an information sheet that they may have at their disposal and they will be given their consent informed, which they will sign by selecting the box "I wish to participate voluntarily" that will appear at the end of the consent. Finally, they will be asked for a username and password to access the web-app. In other words, the user or pseudonym to access the web-app will be selected by the woman herself.

The selected women will be distributed, in March 2022, between the intervention (IG) and control (CG) groups using the simple randomization method and with a 1:1 ratio.

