3.2.2. Specific Objetive

- Evaluate adherence to behavioral recommendations before and after after the educational intervention for each group separately.
- To compare adherence to behavioral recommendations after the intervention between the intervention and control groups.
- Evaluate, in each group separately, the knowledge in relation to the risk factors and symptoms of breast cancer before and after the intervention.
- To compare the level of knowledge in relation to the risk factors and symptoms of breast cancer between the intervention and control groups before and after the intervention.
- Estimate the risk and self-perception of developing breast cancer before and after the intervention for each of the groups.
- To compare the risk and self-perception of developing breast cancer between the intervention and control groups after the educational intervention.

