4.3. Data collection: tools and procedure

The data collection will take place during the months of March (pre-test) and June 2022 (post-test). At both times it will be done virtually, using a digital form. Participants will access this form through the project's web-app. The pre-test collection will be carried out after signing the consent and the post-test, after the educational intervention, that is, at 12 weeks.

At both moments, information will be collected related to personal, anthropometric, and behavioral variables (diet and physical activity), self-examination, knowledge related to risk factors and symptoms of breast cancer, perception of risk of developing breast cancer, and barriers to carry out. take actions to prevent it.

Additionally, after the educational intervention, satisfaction with the use of the web-app will be evaluated.

The information on the behavioral variables will be recorded using the Motiva.Diaf questionnaire. It includes 12 items that measure adherence to and motivation to carry out recommendations related to nutrition (questions 1 to 7) and physical activity (questions 8 to 12). Each item presents a Likert-type response format with a range from 0 (lack of motivation to make the recommendation) to 5 (intrinsic motivation). In addition, each separate recommendation can be interpreted dichotomously (makes=1 or does not make the recommendation=0). Finally, the synthetic variable adherence to healthy recommendations is elaborated as a result of scoring each item in its dichotomous interpretation (range 0=worst adherence to healthy recommendations to 12=greatest adherence to healthy recommendations).

The self-examination is carried out by means of the question, do you perform the breast self-examination once a month.

The information related to knowledge, risk perception and barriers with the MARA questionnaire. This questionnaire, specifically related to breast cancer, consists of 31 items that measure the following constructs: knowledge related to risk factors (9 items), knowledge related to signs and symptoms (9 items), perception of risk of developing breast cancer breast (6 items) and perceived barriers to carry out prevention strategies (7 items). Items related to knowledge have a score of 0 (error) and 1 (correct), therefore the range of scores, both for risk factors and for signs and symptoms, is between 0 and 9. The score of the other two scales is represented on a Likert-type scale ranging from 1

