(totally disagree) to 5 (totally agree), the total perception score being between 6 and 30 points (the lower the score, the lower the perception of risk and the barriers between 7 and 35 points (the lower the score, the fewer perceived barriers).

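### The ±5-point precision that justifies 361 women is for one percentage in one undivided sample; it does not hold for the 1:1 comparison that the trial is designed to make

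*Combined protocol and SAP*

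**What the plan says.** Section 4.2 (Study population) contains the whole sample-size justification: "A random sample of 361 women will be sufficient to estimate, with 95% confidence and an accuracy of +/- 5 percentage units", where the target is "a population percentage that is expected to be approximately 75" per cent. It does not say what this is a percentage of. It adds: "The percentage of necessary replacements has been predicted to be 20" per cent. The same section then divides the women "between the intervention (IG) and control (CG) groups using the simple randomization method and with a 1:1 ratio".

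Section 3.2.2 lists six specific objectives. Three are evaluated within each group, for example "Evaluate adherence to behavioral recommendations before and after after the educational intervention for each group separately". Three are between groups, for example "To compare adherence to behavioral recommendations after the intervention between the intervention and control groups". None asks for a percentage in the pooled sample.

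Section 4.3 defines most outcomes as scores: adherence ("range 0=worst adherence to healthy recommendations to 12=greatest adherence to healthy recommendations"), two knowledge scales from 0 to 9, risk perception ("the total perception score being between 6 and 30 points") and barriers from 7 to 35. The binary measures are the individual diet and activity recommendations, which may be read as yes/no, and the monthly self-examination question. Section 5 sets significance at p ≤ 0.05. No section gives a power, a target difference, a standard deviation or a number per arm.

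**The concern.** A half-width for one percentage in one sample is a survey criterion. Once the sample is split in two, each arm has about half the women, and a difference between arms carries the sampling error of both. The precision that makes 361 sufficient in Section 4.2 is therefore not the precision of any between-group result.

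Two things are at stake. A reader could take ±5 points as the margin on the trial's comparison, when for a percentage near 75% the margin is about twice that. And because the plan states no detectable difference, a non-significant comparison could not be interpreted: nobody could say from the plan what size of effect had been within reach.

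**Working it through.** **Inputs from Section 4.2:** p = 0.75; half-width d = 0.05; 95% confidence (z = 1.96); 20% replacements; total 361; allocation 1:1.

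**Step 1. Reproduce 361.**
- n = z² p(1 − p) / d² = 1.96² × 0.75 × 0.25 / 0.05² = 288.1
- 288.1 / (1 − 0.20) = 360.1, rounded up to 361

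The figure reproduces exactly as a one-sample calculation with the 20% already inside it. This is likely but not certain: rounding first to 289 gives 289 / 0.8 = 361.25, that is 362, and the text does not say how the 20% was used.

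**Step 2. Numbers per arm.**
- No loss, or the 20% added on top of 361: 361 / 2 = 180.5, taken as 180
- 20% lost from 361 after randomisation: 361 × 0.8 / 2 = 144.4, taken as 144

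**Step 3. Percentages, assuming 75% in each arm.**

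| Quantity | Formula | 180 per arm | 144 per arm |
|---|---|---|---|
| One arm, one time point | 1.96 × √(0.1875 / n) | ±6.3 points | ±7.1 points |
| Between-group difference | 1.96 × √(2 × 0.1875 / n) | ±8.9 points | ±10.0 points |

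Simple randomisation hardly changes this. An uneven 162/199 split of 361 gives 1.96 × √(0.1875 × (1/162 + 1/199)) = ±9.0 points.

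**Step 4. Mean scores, in SD units, unadjusted post-intervention comparison.**
- Half-width 1.96 × √(2 / n): 0.21 SD (180), 0.23 SD (144)
- Detectable difference, assuming 80% power and a two-sided 5% two-sample t-test: 0.30 SD (180), 0.33 SD (144)

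The power, the two-sidedness and the t-test are planning assumptions; the plan gives only p ≤ 0.05.

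**The case against.** **The 75% belongs to no named outcome.** This stands. Most outcomes are scores, and neither the yes/no recommendations nor the self-examination question is tied to 75%. The percentage half-widths are therefore illustrations. They also assume equal percentages: at 75% against 85% (an assumed pair) the half-width is 1.96 × √((0.1875 + 0.1275) / n), that is ±8.2 points (180) or ±9.2 (144). The objection does not rescue the ±5, which says even less about a 0–12 score.

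**The replacements may not be losses after randomisation.** This also stands. The sentence sits in the recruitment paragraph, before allocation is described, and could mean replacing invited women who do not take part. The 144-per-arm figures hold only if the 20% are losses after randomisation from within 361.

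**Baseline adjustment would help the score comparison.** Section 5 plans linear regression of post-intervention scores but does not list the predictors. If baseline were included, the detectable difference would shrink by √(1 − r²): to about 0.26 or 0.29 SD at an assumed correlation r of 0.5, and 0.21 or 0.24 SD at 0.7. The figures of 0.30 and 0.33 must be labelled unadjusted.

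**A before/after change within one arm could reach ±5 points.** With 75% at both times the half-width is 1.96 × √(2 × 0.1875 × (1 − r) / n), which is 5 points or less only if r is at least about 0.69 (180) or 0.75 (144). The plan gives no correlation, and this does not bear on the between-group comparison.

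**Stronger readings.** A reader might infer that the trial is too small, or that 361 was miscalculated. The documents support neither. The arithmetic is right for the purpose it states, and without a target difference there is nothing to be underpowered for. A half-width of ±5 on the difference itself would need 1.96² × 2 × 0.1875 / 0.05² = 576.2, so 577 women per arm, but the plan never sets that target and it should not be read as a requirement.

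**Conclusion.** The sample size is not justified for the comparison the trial makes. The ±5-point precision applies to one percentage in an undivided sample. It holds neither for one arm's percentage at a single time point nor for the difference between arms, where it understates the margin by about half. This rests on percentages near 75% in both arms, an unadjusted comparison and 144 to 180 women analysed per arm. The range covers both the case without loss and the case where 20% of 361 are lost, so the conclusion does not depend on which applies.

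It is a gap in justification and a misleading stated precision, not evidence of an inadequate design. For a score, a detectable difference of about a third of a standard deviation may be quite acceptable; the plan does not let a reader judge. It should be fixed, and the fix is small.

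**What to change.** Keep 361 and replace the ±5-point sentence in Section 4.2 with the precision of the two-group comparison, for example:

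> 361 women are randomised 1:1. For an unadjusted post-intervention comparison of a mean score, the 95% half-width is about 0.21 SD with 180 analysed per arm, or 0.23 SD with 144. Assuming 80% power and a two-sided 5% test, the detectable difference is about 0.30 or 0.33 SD, and smaller if the baseline score is adjusted for. For a percentage near 75% in both arms, the half-width of the difference is about ±9 or ±10 points.

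The sponsor should also:
- name the outcome the calculation refers to, and say whether a difference of that size is plausible and worthwhile;
- say what the 75% is a percentage of;
- state whether the 20% is inside 361, and whether it means losses after randomisation or non-participation before it. If 361 is not the number randomised, the first sentence of the text must change. The 144-per-arm figures stay only if the 20% are post-randomisation losses inside 361.

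The cost is one paragraph and these decisions. No women are added, and the allocation and planned tests stay as they are; the 80% power and the test are for planning only. There are two drawbacks. The stated precision becomes less favourable. And a detectable difference worked back from a fixed number documents that number rather than justifying it, so the sponsor still has to defend the effect size.

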5. STATISTICAL ANALYSIS

Initially, the normality of the distribution of the variables will be verified, the Kolmogorov-Smirnov test will be used. A description of the variables will be made using percentages, means (standard deviation) or median (interquartile range) depending on their nature and distribution.

To determine the association between variables, the chi-square test, McNemar for qualitative variables, will be used. For qualitative variables, they will be determined based on the distribution of variables.

Linear regression analyzes will be carried out to determine which variables best predict the score after the intervention in terms of knowledge about risk factors, signs-symptoms of early detection of breast cancer, knowledge and adherence to healthy behaviors.

The analyzes will be carried out using the IBM SPSS version 24.0®, considering that the results were statistically significant when the value of p is ≤ 0.05 .

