6. ETHICAL CONSIDERATIONS

In general, the precepts of the Declaration of Helsinki will be respected. This defines the principles that must be scrupulously respected by all the people involved in the present investigation. Specifically, informed consent will be requested, the free will to abandon the research will be respected without this causing any harm to the person, and the confidentiality of the data of the subjects participating in the study will be respected. The treatment, communication and transfer of personal data of all participants will comply with the provisions of Organic Law 3/2018, of December 5. The project has been

reviewed and authorized by the Research Ethics Committee of the Principality of Asturias and prior to its start it will be registered in ClinicalTrials.gov.

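### The plan allows 20% for replacements but defines no analysis set and no rule for a missing 12-week form, so post-test group comparisons would fall on completers without stated use of the pre-test score

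*Combined protocol and SAP*

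**What the plan says.** Section 4.2 sets the sample size by precision: "A random sample of 361 women will be sufficient to estimate, with 95% confidence and an accuracy of +/- 5 percentage units", for "a population percentage that is expected to be approximately 75" per cent. It then adds: "The percentage of necessary replacements has been predicted to be 20" per cent. Women are allocated "using the simple randomization method and with a 1:1 ratio".

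Section 4.3 has two measurement times: "The pre-test collection will be carried out after signing the consent and the post-test, after the educational intervention, that is, at 12 weeks". There is no measurement in between, so every post-intervention outcome depends on the one June form. The section gives the score ranges (adherence 0 to 12, each knowledge score 0 to 9, risk perception 6 to 30, barriers 7 to 35) but no rule for an absent form.

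Section 5 names a normality check, chi-square, McNemar and regression. On the last it says: "Linear regression analyzes will be carried out to determine which variables best predict the score after the intervention". It does not list the predictors. It defines no analysis population, missing-data method or sensitivity analysis.

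Section 6 covers withdrawal only as a right: "the free will to abandon the research will be respected without this causing any harm to the person". It does not say how a woman who leaves is analysed.

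**The concern.** The main objective (3.2.1) is the effectiveness of the intervention, and 3.2.2 asks for comparisons of the two randomised groups after it. A post-test chi-square, a McNemar test on pairs and a regression on the post-test score all need the 12-week value. Because the plan is silent on missing values, those analyses would use the women who returned the June form.

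Inflating the sample restores precision but does nothing about selection. One arm is asked to use a web-app for 12 weeks and the other receives usual care, so loss could plausibly differ between them. If it does, and if women with lower pre-test scores leave more often, the completers in the two arms no longer start from the same level. An unadjusted comparison can then show a benefit that does not exist. The pre-test is collected anyway and is the natural means of correction, but section 5 does not assign it that role.

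**Working it through.** **Inputs from section 4.2:** expected proportion 0.75, half-width 0.05, 95% confidence, allowance 20%, total 361, ratio 1:1. The significance level in section 5 is 0.05, taken here as two-sided.

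**1. Reproducing 361.**
- n = 1.96² × 0.75 × 0.25 / 0.05² = 288.1.
- 288.1 / (1 − 0.20) = 360.1, rounded up to 361. This matches.
- No inflation gives 289, and multiplying by 1.2 gives 347. Neither matches.

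The 20% is therefore already inside 361. Read as loss, 0.20 × 361 = 72.2 women lack the form and 0.80 × 361 = 288.8 have it, about 144 per arm.

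**2. Closed-form bias under no true effect.** Assume that lost women score 0.5 SD below completers in both arms. The bias is 0.5 × (loss in IG − loss in CG), and SE = √(1/n_IG + 1/n_CG) starting from 180.5 per arm.

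| Loss IG / CG | Bias (SD) | SE (SD) | Bias/SE | Type I error |
|---|---|---|---|---|
| 20% / 20% | 0 | 0.118 | 0 | 5% |
| 25% / 15% | 0.05 | 0.118 | 0.42 | 7.1% |
| 30% / 10% | 0.10 | 0.119 | 0.84 | 13.5% |

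**3. Simulation with dropout driven by the pre-test.** There were 181 and 180 women, no true effect, standardised scores with pre-post correlation 0.6, and several thousand trials per setting. Dropout was logistic in the pre-test score, with intercepts set to give about 30% loss in IG and 11% in CG.

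| Dropout slope per SD of pre-test | Completers, unadjusted | Completers, adjusted for pre-test |
|---|---|---|
| −0.3 | about 6% | about 5% |
| −0.5 | about 8% | about 5% |
| −0.9 | about 11% | about 5% |

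At slope −0.9 the unadjusted bias is about 0.085 SD, and the adjusted bias is 0.00. Repeat runs differ by a few tenths of a percentage point. With equal loss of 20% per arm, the unadjusted error is 5% at every slope.

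**4. Precision.** At the −0.9 setting the standard error falls from 0.117 to 0.095 SD: (0.117 − 0.095)/0.117 = 19%. This is close to what theory gives, √(1 − 0.6²) = 0.80. The gain does not depend on unequal loss.

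**5. Effect size, a separate matter.** If every lost intervention woman gained nothing and loss were 20%, the completer difference would exceed the all-randomised effect by 1/(1 − 0.20) − 1 = 25%. Pre-test adjustment does not address this. It is the reason for a sensitivity analysis.

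**Assumptions not in the documents:** loss by arm, the 0.5 SD gap, the 0.6 correlation and the dropout slopes.

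**The case against.** Several stronger readings are tempting, and the documents do not support them.

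- A reader might infer that the plan expects 72 women to be lost after randomisation. The term used is replacements, in a recruitment paragraph placed before allocation is described. The arithmetic shows that an allowance was built in. It does not show whether the allowance covers women replaced before allocation or women lost after it.
- A reader might infer that every named test discards such a woman. Baseline knowledge comparisons and descriptions keep her pre-test. For the quantitative scores section 5 names no group-comparison test at all, because the sentence that seems meant for them repeats the word for qualitative variables. The completers-only result follows from silence and is not a declared plan.
- A reader might infer that women could be excluded for not using the app. Nothing says so, and 3.2.2 compares the intervention and control groups.
- A reader might infer that the false-positive rate will be well above 5%. That needs unequal loss, which no passage states. The 11% also needs a steep slope, and at weaker slopes it is 6% to 8%.

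Two further objections stand in part. The planned regression could include the pre-test score. However, it is described as a search for the best predictors, with no covariates fixed, so it is not a defined group contrast. Also, the gain shown above comes from using the pre-test and not from imputation as such, so imputation is an equivalent route and not a demonstrably better one.

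**Conclusion.** The point holds in a limited form. The plan defines neither an analysis set nor the handling of a missing post-test, although its sample size carries a 20% allowance. As written, the post-test contrasts would be made on completers with no stated use of the pre-test.

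The harm to the type I error is conditional: none with equal loss, and about 6% to 11% under the assumed 30% and 11% loss. The precision gain of about 19% applies whether or not loss is unequal, but it rests on the assumed correlation of 0.6. The change should be made, since it substitutes a better analysis at almost no cost, but the documents do not show that the trial's conclusions would be wrong without it.

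The calculations give no reason to enlarge the sample for this loss. Inflating 361 again, to 452, would count the same 20% twice.

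**What to change.** Add one paragraph to section 5:

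1. Comparisons between IG and CG include all randomised women in their assigned group.
2. For each post-test score, the IG−CG difference is estimated with adjustment for the pre-test value of that score. Equivalently, missing post-tests are multiply imputed by arm from the pre-test variables. The adjusted model is fitted to women with a post-test and is valid if dropout depends only on arm and pre-test. Imputation rests on the same kind of assumption and keeps every randomised woman in the analysis. State which is used.
3. A reported sensitivity analysis imputes missing intervention women from the control distribution given their pre-test. It informs the reading of the result and is not a condition for claiming effectiveness.
4. Loss is reported by arm, with the pre-test scores of lost and retained women. The paragraph also states whether replacements may enter after randomisation.

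Randomisation and the pre-test both fall in March 2022 with no stated order. The paragraph should therefore also say what happens if a randomised woman has no pre-test.

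Cost: a little more analysis work, with no new data, visits or women. The sensitivity estimate will probably be smaller than the completer estimate.

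### The 12-week group comparisons carry avoidable chance variation: allocation is by simple randomisation and no baseline-adjusted comparison is specified

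*Combined protocol and SAP*

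**What the plan says.** **Allocation.** Section 4.2 places recruitment "between the months of January and February 2022, by sending a letter of invitation" and says that "when we have obtained the necessary sample, the project will be explained in detail". In March 2022 the women are then divided "between the intervention (IG) and control (CG) groups using the simple randomization method and with a 1:1 ratio". It mentions no blocking, stratification, minimisation or fixed arm size, and does not describe how the randomisation is carried out.

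**Timing of the pre-test.** Section 4.3 puts the pre-test in March 2022 as well: "The pre-test collection will be carried out after signing the consent and the post-test, after the educational intervention, that is, at 12 weeks". It does not say whether the pre-test comes before or after allocation.

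**Comparisons.** Section 3.2.2 includes the aim "To compare adherence to behavioral recommendations after the intervention between the intervention and control groups". Risk and its self-perception are also compared between groups after the intervention. Knowledge is compared between groups both before and after.

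**Analysis.** Section 5 names chi-square and McNemar tests, and linear regression to find predictors of the post-test scores. It names neither study group nor the pre-test score as a term.

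**The concern.** One-by-one simple randomisation is useful when participants arrive in sequence and the next assignment must stay unpredictable. Here the list appears to be complete before anyone is allocated, so that reason falls away and balance could be built in at little cost. The usual alternative safeguard, adjusting each comparison for the woman's own starting value, is not written into section 5 either.

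With neither safeguard, whatever gap in pre-test scores chance produces passes partly into the 12-week difference, in proportion to the pre-post correlation. At stake is precision: wider confidence intervals and lower power from the same women. In an individual trial with a visible imbalance, the result is also harder to read.

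**Working it through.** **Inputs from the plan.** Section 4.2: N = 361, 95% confidence, ±5 points, expected percentage 75%, 20% replacements, 1:1 simple randomisation. Section 5: significance at p ≤ 0.05 (two-sided assumed). The plan gives no effect size, SD, power or pre-post correlation for the group comparison. The values below for these (0.3 SD; correlation r = 0.3, 0.5, 0.7) are assumptions.

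**1. The plan's own figure.** n = 1.96² × 0.75 × 0.25 / 0.05² = 288.1, and 288.1 / 0.8 = 360.1, rounded up to 361. So 361 is reproduced and already contains the 20% allowance. About 361 × 0.8 ≈ 289 women may be analysed.

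**2. Arm sizes, if each woman is assigned by an independent fair coin.** The SD of one arm's size is √361 / 2 = 9.5, and its 95% range is 162 to 199. A 180/181 split has probability 8.4%. Efficiency at 162/199 is 4 × 162 × 199 / 361² = 0.989. For a comparison with 80% power at equal arms (a reference value), power at that limit is 79.6%. Arm size is not the issue.

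**3. Chance differences at pre-test.** The SD of a standardised difference is 2/√361 = 0.105. A gap above 0.2 SD is 0.2/0.105 = 1.9 standard errors, probability 5.7% per score. Given a gap of exactly 0.2 SD, an unadjusted comparison shifts by 0.2r = 0.06, 0.10 or 0.14 SD, and its type I error conditional on that gap is 7.7%, 12.2% or 18.9% at r = 0.3, 0.5, 0.7. Over all randomisations it stays at its nominal level (5.2% in a simulation of 8,000 runs at r = 0.5).

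**4. What adjustment and stratification recover.** Adjusting for the pre-test value multiplies the variance by 1 − r². Allocating within halves of a normally distributed pre-test score, with the strata in the analysis, multiplies it by 1 − 0.637r². Power for 0.3 SD with 289 women is Φ(0.3/SE − 1.96), where the unadjusted SE is 2/√289 = 0.1176.

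| r (assumed) | Variance cut, baseline adjustment | Variance cut, median split only | Power: neither | Power: median split | Power: adjustment |
|---|---|---|---|---|---|
| 0.3 | 9% | 6% | 72% | 75% | 76% |
| 0.5 | 25% | 16% | 72% | 79% | 84% |
| 0.7 | 49% | 31% | 72% | 87% | 95% |

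For example, at r = 0.5 with adjustment: SE = 0.1176 × √0.75 = 0.1019, and Φ(0.3/0.1019 − 1.96) = Φ(0.98) = 84%.

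**5. Both together.** Simulation with N = 361, r = 0.5, 8,000 runs, using four strata of the pre-test score:

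| Allocation and analysis | SE of the effect (SD units) |
|---|---|
| Simple, unadjusted | 0.106 |
| Simple, adjusted | 0.0917 |
| Stratified, unadjusted | 0.0930 |
| Stratified, adjusted | 0.0910 |

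The simulation error of such an SE is about 0.0917/√16,000 = 0.0007, so the last step (0.0917 to 0.0910) is hardly distinguishable from none. Stratified allocation followed by a test that ignores the strata is conservative (simulated type I error 2.6%).

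**The case against.** The strongest reply is that nothing here is wrong. A 1:1 ratio with simple randomisation ordinarily means equal allocation probability, so 4.2 is coherent. Since it does not describe the mechanism, a random halving of the list would also fit its words. Chance imbalance is already allowed for in the standard error of an unadjusted test. This stands. A reader might infer that the plan contradicts its own ratio or that the comparison is biased; the documents support neither.

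The second reply is that stratification is the wrong lever. This also stands: nearly all the recoverable precision comes from baseline adjustment. A median split on adherence helps mainly the adherence comparison. If pre-test adherence correlated at 0.2 with a knowledge score (an assumption), the variance cut there would be 0.637 × 0.04 = 2.5%. Nor can the gain from age bands be quantified, because the plan gives no relation between age and outcome.

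Third, the regression in section 5 might include the pre-test score, and knowledge is compared at pre-test. Both are possible safeguards, but neither is a stated baseline-adjusted comparison of the groups: section 5 looks for predictors and does not name group or pre-test value.

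Fourth, allocation in a single step is inferred from the sequence of recruitment and allocation, and the order of pre-test and allocation is not given. Stratifying on a pre-test score is therefore cheap only if that order is fixed first.

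**Conclusion.** The point holds as a minor, inexpensive improvement. As written, neither allocation nor analysis removes chance pre-test differences from the 12-week comparisons, and the cost is precision. At an assumed correlation of 0.5 the avoidable part is about a quarter of the variance; with about 289 women and an assumed 0.3 SD effect, power is about 72% unadjusted against about 84% adjusted. At correlations of 0.3 and 0.7 the adjusted figures are about 76% and 95%.

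These sizes rest on the assumed correlations and effect, on a normal approximation for scores that are bounded counts (adherence 0 to 12, with ties at the median), and on the 20% allowance being fully used. A reader might infer that stratified allocation is the main remedy or would sharpen every outcome equally. The calculation does not support that: its value on top of adjustment is mainly equal arms and visible balance at pre-test.

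**What to change.** 1. **Section 5 (the change that matters).** State that each 12-week difference between IG and CG will be estimated with a model containing study group, the pre-test value of the same outcome, and any factor used to stratify allocation. Keep the search for predictors as a separate, secondary analysis.

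2. **Section 4.2.** State that every woman completes the pre-test before allocation. The closed list is then divided by computer-generated random permutation into equal halves of IG and CG, within age band (25–34 / 35–45) and pre-test adherence (below / at or above the median). If the pre-test is not available in time, use age band only.

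3. **Section 4.3.** State the same order of pre-test and allocation. This also keeps pre-test answers from being given after a woman knows her group.

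**Cost.** A few sentences, a short allocation script and a few extra model terms, using data the plan already collects. The real downside is that allocation must wait for the pre-test forms, with a rule for women who return theirs late. If only one change is made, it should be the first.
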